#### **5.4.10.2 Uses of Warfarin or Other Coumadin-Derived Anticoagulants**

Use of warfarin or other coumadin-derived anticoagulants should be avoided during treatment with poziotinib. When it cannot be avoided, regular monitoring of INR is required and prior authorization from study medical monitor is required.

#### **5.4.10.3 Other Anticancer Therapies**

No additional cytotoxic agents, biologic therapy, or immune response modifiers for cure-intent purpose are to be administered to patients until study treatment has been discontinued.

#### 5.4.10.4 Prohibited Therapies or Medications

No other anti-cancer therapy, including chemotherapy, radiation therapy, immunotherapy, or experimental medications, are permitted during the trial. Any disease progression that requires anti-tumor therapy will be cause for discontinuation from the study.

### 6 STUDY DRUG AND PHARMACEUTICAL INFORMATION

Study treatment is to be handled and administered according to the study sites' regulations for the handling and administration of cytotoxic anticancer agents.

#### 6.1 Poziotinib

Poziotinib will be supplied by Spectrum.

##### 6.1.1 Poziotinib Composition

The poziotinib drug substance is a hydrochloride salt of poziotinib and is formulated as a tablet for oral administration.

##### 6.1.2 Poziotinib Supply and Labeling

Poziotinib tablets are supplied in 2.0-mg and 8.0-mg dose strengths, and contain 2.0 mg and 8.0 mg of poziotinib hydrochloride salt, respectively.

##### 6.1.3 Poziotinib Administration

Poziotinib is supplied as 8-mg and 2-mg tablets and will be administered orally once daily at approximately the same time each morning according to the schedule for each cohort during each 21-day cycle. If the morning dose is missed, this dose may be administered any time during the day, at least 8 hours prior to the next scheduled dose.

- **Cohort 1:** 24 mg (three 8-mg tablets) for 14 days and then 7 treatment-free rest days
- **Cohort 2:** 16 mg (two 8-mg tablets) once daily continuously
- **Cohort 3:** 12 mg (one 8-mg tablet and two 2-mg tablets) once daily continuously

##### 6.1.4 Poziotinib Storage and Handling

Poziotinib supplies must be stored in a secure, limited-access location under the storage conditions specified on the drug supply label.

KEEP THIS AND ALL MEDICATIONS OUT OF THE REACH OF CHILDREN.

##### 6.1.5 Poziotinib Dose Modifications

- After the first occurrence of an AE Grade  $\geq 3$ , the dose of poziotinib will be temporarily withheld. Once the event has recovered to Grade  $\leq 1$ , the treatment can resume at the same dose.
- If the same AE occurs a second time (Grade  $\geq 3$ ), the dose of poziotinib will be reduced.
- No dose reductions below 12 mg/day will be allowed.

An algorithm for poziotinib dose modification is provided in [Table 2](#).

**Table 2 Poziotinib Dose Modifications**

Adverse Event	Grade	1st Occurrence	2nd Occurrence	3rd Occurrence
Diarrhea	Grade $\geq 3$ (Despite adequate anti-diarrheal prophylaxis and/or treatment)	Poziotinib Dose stays the same	Poziotinib Dose Reduced: 24 mg $\rightarrow$ 16 mg 16 mg $\rightarrow$ 12 mg 12 mg dose - discontinue treatment	Poziotinib Dose Reduced: 16 mg $\rightarrow$ 12 mg 12 mg dose - discontinue treatment
	Grade $\geq 2$ for $\geq 48$ hours (Despite adequate anti-diarrheal prophylaxis and/or treatment)			
Rash	Grade $\geq 3$	Poziotinib Dose stays the same	Poziotinib Dose Reduced: 24 mg $\rightarrow$ 16 mg 16 mg $\rightarrow$ 12 mg 12 mg dose - discontinue treatment	Poziotinib Dose Reduced: 16 mg $\rightarrow$ 12 mg 12 mg dose - discontinue treatment
Nausea and/or Vomiting	Grade $\geq 3$ (Despite adequate anti-emetics) Grade $\geq 2$ for $\geq 48$ hours (Despite adequate anti-emetics)	Poziotinib Dose stays the same	Poziotinib Dose Reduced: 24 mg $\rightarrow$ 16 mg 16 mg $\rightarrow$ 12 mg 12 mg dose - discontinue treatment	Poziotinib Dose Reduced: 16 mg $\rightarrow$ 12 mg 12 mg dose - discontinue treatment
LVEF Dysfunction	Grade $\geq 3$	Discontinue Treatment		

## 6.2 Comparator Treatment

No comparator is used in this study.

## 7 SAFETY ASSESSMENT

### 7.1 Safety Measures

It is the responsibility of the Principal Investigator to oversee the safety of the patients at their site and to report all AEs/SAEs that are observed or reported during the study, regardless of relationship to study drug or clinical significance. The decision to modify the dose of study treatment will be determined by the Investigator based on the decision rules shown in [Section 6.1.5](#).

Safety data will also be reviewed on a regular basis by Spectrum's study monitoring team, which includes a Clinical Research Associate (CRA), Medical Monitor, and other personnel from the company or its designee.

Adverse events will be characterized by intensity (severity), causality, and seriousness by the Investigator based on the regulatory definitions included below.

This study will utilize the National Cancer Institute (NCI) Common Terminology Criteria for Adverse Events (CTCAE) Scale Version 4.03 for AE grading.

## 7.2 Adverse Events

An AE is defined as any untoward medical occurrence in a patient or clinical investigation patient, temporally associated with the use of a medicinal product, whether or not considered related to the medicinal product. Therefore, an AE can be any unfavorable and unintended sign (including an abnormal laboratory finding), symptom, or disease (new or exacerbated) temporally associated with the use of a medicinal product. A treatment-emergent AE (TEAE) is any AE that occurs from the first dose of study treatment until 35 ( $\pm 5$ ) days after the last dose of study treatment.

The study will record all AEs according to the information in [Section 7.3](#).

Examples of AEs **include**:

- Exacerbation of a chronic or intermittent pre-existing condition including either an increase in frequency and/or intensity of the condition.
- New conditions detected or diagnosed after investigational product administration.
- Signs, symptoms, or the clinical sequelae of a suspected drug interaction.
- Signs, symptoms, or the clinical sequelae of a suspected overdose of either investigational product or a concurrent medication.
- AEs may include pre-treatment or post-treatment events that occur as a result of protocol-mandated procedures, ie, invasive procedures.

Abnormal laboratory results are to be recorded as AEs, if any of the following conditions are met:

- The abnormal laboratory value leads to a therapeutic intervention.
- The abnormal laboratory value is considered to be clinically significant by the Investigator.
- The abnormal laboratory value is predefined as an AE in the protocol or in another document communicated to the Investigator by Spectrum or designee.

Examples of events that **do not** constitute AEs include:

- Medical or surgical procedures (eg, endoscopy, appendectomy); the condition that leads to the procedure is an AE.
- Situations where an untoward medical occurrence does not occur (eg, social and/or convenience admission to a hospital).
- Anticipated day-to-day fluctuations of pre-existing disease(s) or condition(s) present or detected at the start of the study that do not worsen.
- Planned and prescheduled hospitalizations and procedures.
- Progressive disease.

The adverse events of special interest identified with poziotinib treatment in this study include diarrhea, skin rash, oral cavity mucositis/stomatitis, fatigue, and vomiting/nausea.

### 7.3 Guidelines for Recording and Attribution Scoring of Adverse Events

Timely and complete reporting of all AEs is required for all patients. Monitoring and documentation of all AEs allows for identification of potential study-drug or dose-related AEs, and for adherence to regulatory requirements. Please refer to the CRF Completion Guidelines located in the study binder for detailed instructions for AE reporting.

#### 7.3.1 Recording of Adverse Events

All AEs that occur from the first dose of study treatment through 35 ( $\pm$ 5) days after the last dose of study treatment is administered are to be recorded on the AE CRF. From the time the study Informed Consent is signed through the first dose of study drug administration, only SAEs that are related to study procedures are to be recorded.

The resolution of all AEs must be recorded at the end of the study. The following conventions will be followed when patient completes or discontinues from the study:

- If a patient dies, the date of death should be the date of AE stop for all ongoing AEs at the time of death.
- If a patient discontinues due to an AE(s), the outcome of the AE is to be followed for 35 ( $\pm$ 5) days from the date of discontinuation or until the AE has returned to Grade  $\leq$ 1. The status of the AE and the date of last contact with the patient will be captured. If the AE has not returned to Grade  $\leq$ 1 by the end of the study, the AE stop date should be left as ongoing.

All AEs will be classified by intensity/severity (**Section 7.3.2**), relationship to study drug (**Section 7.5**), and as serious or nonserious (**Section 7.7**) by the Investigator.

#### 7.3.2 Grading of Adverse Events

This study will utilize the NCI CTCAE Scale, Version 4.03 for AE grading.

### 7.4 Follow-up of Adverse Events

All AEs and significant abnormal laboratory values are to be followed up in accordance with the International Conference on Harmonization (ICH) Good Clinical Practice (GCP) guidelines, and other applicable regulatory requirements (eg, United States [US] Code of Federal Regulations [CFR]).

### 7.5 Relationship

The Investigator must make a causality assessment and document their opinion as to the relationship of all AEs and SAEs to study treatment (**Table 3**).

**Table 3 Investigator Assessment of Adverse Event Causality**

Relationship	Description
Not Related	The event is clearly related to factors other than study treatment, such as the patient's clinical state, therapeutic interventions, or concomitant medications administered to the patient.
Unlikely Related	The temporal association, patient history and/or circumstances are such that the study drug or treatment is not likely to have had an association with observed event.
Possibly Related	The event follows a reasonable temporal sequence from the time of study treatment administration, and/or follows a known response pattern to study treatment, but could have been produced by other factors, such as the patient's clinical state, therapeutic interventions, or concomitant medications administered to the patient.
Probably Related	The event follows a reasonable temporal sequence from the time of study treatment administration, and follows a known response pattern to study treatment, and cannot be reasonably explained by other factors, such as the patient's clinical state, therapeutic interventions, or concomitant medications administered to the patient.
Definitely Related	The event follows a reasonable temporal sequence from the time of study treatment administration, and follows a known response pattern to study treatment, and cannot be reasonably explained by other factors, such as the patient's clinical state, therapeutic interventions, or concomitant medications administered to the patient.

In addition, the event either occurs immediately following study treatment administration, improves on stopping study treatment, reappears on repeat exposure, or there is a positive reaction at the application site.

## 7.6 Expectedness

For investigational drugs, an AE is judged "expected" if its description agrees in nature and severity with the description of AEs previously noted with the study drug as detailed in the current Investigator's Brochure. An "unexpected" AE is one for which the specificity or severity is neither consistent with the current Investigator's Brochure nor the risk information described in the general investigational plan. The Sponsor will be responsible for assessing the expectedness of AEs.

The most common AEs associated with poziotinib treatment include:

- Diarrhea
- Rash
- Stomatitis
- Fatigue
- Vomiting
- Decreased Appetite
- Dry Skin
- Nausea

## 7.7 Serious Adverse Events

In the interest of patient care and to allow Spectrum to fulfill all regulatory requirements, any SAE, regardless of causal relationship to study treatment, is to be reported to the Sponsor within 24 hours of knowledge of the event. SAEs are defined (21 CFR 312.32, ICH of Technical Requirements for Registration of Pharmaceuticals for Human Use E2A Guideline) as those AEs that meet any of the following criteria:

- Results in death.
- Is life-threatening: ie, any event that, in the opinion of the Investigator, poses an immediate risk of death from that event.
- Requires inpatient hospitalization or prolongation of existing hospitalization (excluding hospitalizations for study therapy, disease-related procedures, or placement of an indwelling catheter, unless associated with other SAEs).
- Results in a persistent or significant disability/incapacity.
- Results in a congenital anomaly/birth defect.
- Includes important medical events that may not be immediately life threatening or result in death or hospitalization but may jeopardize the patient or may require intervention to prevent one of the outcomes listed in this definition.

Adverse events that do not meet any of the above criteria for serious should be regarded as non-serious.

### 7.7.1 Serious Adverse Event Reporting

From the time the study Informed Consent is signed through the first dose of study drug administration, only SAEs that are related to study procedures are to be recorded. All SAEs that occur from the first dose of study drug administration through 35 ( $\pm$ 5) days after the last dose of study treatment are to be reported to Spectrum within 24 hours of knowledge of the event.

SAEs (regardless of their relationship to study treatment) are to be reported and the serious adverse event report (SAER) faxed or e-mailed within 24 hours of knowledge of the event to:

**Spectrum Pharmaceuticals, Inc.**  
**Primary Contact: Pharmacovigilance Department**  
**Fax:** [REDACTED]  
**E-mail:** [REDACTED]

Spectrum may request additional information from the Investigator to ensure the timely completion of accurate safety reports. Safety data that are critical to the reportability of an SAE, such as causality assessment and serious criteria, should be included in the initial faxed or e-mailed SAER. If omitted, a timely response to drug safety data queries received from Spectrum or designee is expected.

The Investigator is to take all appropriate therapeutic measures necessary for resolution of the SAE. Any medications necessary for treatment of the SAE are to be recorded in the concomitant medication section of the patient's CRF.

SAEs that are study-treatment related will be followed until resolution or until they have returned to Grade 1, whichever is longer, or until it is determined that the outcome will not change with further follow-up.

Additionally, the SAE is to be entered in the AE section of the CRF. Follow-up SAERs need to be submitted to Spectrum within 24 hours, once additional information regarding the event becomes available (eg, final diagnosis is made, laboratory or test results, event course, outcome, etc).

The Sponsor or its designee will be responsible for reporting SAEs to the regulatory authorities in accordance with applicable expedited reporting regulatory guidelines. The Investigator is responsible for submitting SAEs to his/her Institutional Review Board (IRB)/Ethics Committee (EC). Copies of each SAER, and documentation of IRB/EC notification and acknowledgement of receipt, will be kept in the Site's Regulatory Binder.

### 7.7.2 Exclusions to Serious Adverse Event Reporting Requirements

The following are not considered SAEs:

- Situations where an untoward medical occurrence did not occur (eg, social and/or convenience admission to a hospital, hospitalization for diagnostic tests such as CT scans).
- Anticipated day-to-day fluctuations of pre-existing disease(s) or condition(s) present or detected prior to first study treatment administration that do not worsen.
- Planned and prescheduled hospitalizations and procedures.
- Progressive disease.

### 7.8 Reproductive Risks

No adequate and well-controlled studies of poziotinib have been conducted in pregnant women. The effect of poziotinib on fertility and fetal development have not been studied in pregnant women. Poziotinib is not recommended for use during pregnancy.

Any pregnancy involving a study patient or a patient's partner that occur from the first dose of study treatment through 30 days after the last dose of study treatment is to be reported to the Sponsor within 24 hours after the Investigator has gained knowledge of the event via fax or e-mail (see contact information in [Section 7.7.1](#)). Pregnancies should be followed up until outcome and follow-up information regarding the outcome of the pregnancy should be faxed or e-mailed to Spectrum's Pharmacovigilance Department.

All patients who become pregnant during participation in this study are to be withdrawn from the study.

## 8 STATISTICAL PLAN

This section contains a brief overview of the statistical analyses planned for this study. A formal statistical analysis plan (SAP), providing full technical details, will be finalized prior to database lock.

## 8.1 Sample Size

Other important treatments for HER2-positive MBC include T-DM1, lapatinib-capecitabine combination, and neratinib. Published ORRs reported for these regimens are 43.6%, 30.8%, and 24%, respectively [22, 24-25]. The purpose of this study is to evaluate the safety and efficacy of poziotinib and identify the optimal dose for future clinical development. No statistical hypothesis testing will be performed.

The enrollment into **Cohort 1** is now complete. A total of 32 patients have received treatment of poziotinib in **Cohort 1**. A total of 30 patients are expected to be enrolled and treated in **Cohort 2**. If the enrollment in **Cohort 2** is stopped due to toxicity, new patients will be enrolled into **Cohort 3**. A total of 20 patients will be enrolled in **Cohort 3**.

## 8.2 Method of Treatment Assignment

This study is not randomized. Patients will be enrolled sequentially.

## 8.3 Analysis Populations

Two analysis populations have been defined as follows:

- **The Evaluable Population (EP)** consists of all patients who are enrolled, complete at least one cycle of poziotinib treatment, and have at least one post-baseline tumor response evaluation using RECIST, Version 1.1.
- **The Safety Analysis Population (SAF)** includes all patients who signed informed consent, enrolled, and received at least one dose of study treatment. All demographics, Baseline characteristics, and safety data will be analyzed using the SAF population.

## 8.4 General Statistical Methods

The Sponsor's Biostatistics and Data Management (BDM) group will be responsible for data management and statistical analysis of this study. All statistical analyses will be performed using SAS for Windows (version 9.3 or higher). Patient data listings and tabular presentations of results will be provided. Further details of the criteria and conduct of the statistical analyses will be included in the SAP for this study.

## 8.5 Efficacy Analyses

### 8.5.1 Primary Endpoint

The primary efficacy variables, as described below, will be summarized and analyzed descriptively, along with 95% CI, for each cohort.

- **Objective Response Rate (ORR)** will be assessed according to the Response Evaluation Criteria in Solid Tumors (RECIST) Guidelines, version 1.1 [23] and is defined as the best response [Complete Response (CR) + Partial Response (PR)] recorded from the start of the study until the end of study in patients who received at least 1 dose of poziotinib. The ORR will be based on the EP.

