### 5.3.8 End-of-Treatment Visit (35 $\pm$ 5] Days Post-Study Treatment)

The **End-of-Treatment Visit** is required 35 ( $\pm 5$ ) days after the last dose of poziotinib is administered. The following assessments are to be performed at this visit:

- Physical examination
- Vital signs
- ECOG Performance Status assessment
- Tumor assessment (unless the patient has documented disease progression or has undergone a tumor assessment within the previous 6 weeks)
- CBC with 5-part differential and platelets
- Serum biochemistry
- Echocardiogram or MUGA scan to evaluate cardiac ejection fraction
- Adverse event assessment
- Patient Diary Collection
- Concomitant medications

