#### 4 ANALYSIS POPULATIONS

Two analysis populations have been defined as follows:

- The **Evaluable Population (EP)** consists of all patients who are enrolled, complete at least one cycle of poziotinib treatment, and have at least one evaluable post-baseline tumor response evaluation using RECIST criteria, Version 1.1.
- The **Safety Analysis Population (SAF)** includes all patients who signed informed consent, enrolled, and received at least one dose of study treatment. All demographics, Baseline characteristics, and safety data will be analyzed using the **SAF** population.

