### **5.3 Efficacy Analyses**

All efficacy endpoints will be analyzed based on the Evaluable Population for each cohort.

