#### **5.3.1 Best Overall Response**

Since there is no statistical test of hypotheses in this proof-of-concept study, the overall responses will be provided using various criteria or assessment. The determination of time point overall response will be made by the local site investigator using RECIST criteria, Version 1.1. The determination of best overall response (BOR) will be summarized as below.

1. Per Investigator Assessment: BOR will be summarized as reported by the local investigator. This includes CR, PR, SD, PD or NE. Please note the following:
  - Spectrum will not cross-check or derive the responses based on tumor measurement or time point responses as all BOR will be as reported by the investigator.
  - Local Investigator may not report a CR or PR as confirmed or unconfirmed, or SD adjudicated based on the duration of treatment and will be reported as is.
2. Per Sponsor Derivation: Spectrum will use the detailed tumor data as reported on case report form such as tumor measurements, lesion assessment, duration of treatment, and confirmation scan to derive the time point response and BOR using RECIST criteria, Version 1.1.
  - Time point response will be determined as described in Section 3.3.2 and 3.3.3.
  - BOR with confirmation will be determined as described in Table 2 below.

- BOR without confirmation will not require a confirmation scan for CR/PR or  $\geq 6$  weeks on-treatment.
- If there is a time point with missing tumor measurement, but the time point response is available from site, this time point response will be used for determination of BOR regardless of missing tumor measurement.

Table 1. Determination of Confirmed Best Overall Response

Initial Best Response (can start at any visit)	Response at Subsequent Visit	Best Overall Response
CR	CR 	CR
PR	PR  or unconfirmed CR 	PR
PR	SD (not followed by CR/PR)	SD
SD	SD or unconfirmed CR/PR	SD
CR or PR or SD	PD	SD  or PD 
CR or PR or SD	NE (no additional evaluable visit)	SD  or NE 
PD	Any	PD
NE	NE (no additional evaluable visit)	NE

 Confirmation scan needs to be  $\geq 4$  weeks from previous scan, 1 intervening NE is allowed.

 Confirmation scan needs to be  $\geq 4$  weeks from previous scan, 1 intervening NE/SD is allowed.

 If initial CR/PR/SD is  $\geq 6$  weeks on-treatment.

 If initial CR/PR/SD is  $< 6$  weeks on-treatment.

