### 5.3.3 Secondary Efficacy Endpoints

#### Progression-Free Survival (PFS)

PFS is defined as the number of months from the treatment start date to the date of documented disease progression or death due to any cause. PFS of living patients without documented PD will be censored at the time of last tumor assessment or the date of first treatment if there is no post-baseline tumor assessment.

Distribution of PFS will be estimated using the Kaplan-Meier method in the Evaluable Population. The median and quartiles of PFS and the PFS rate at 3, 6, 9 and 12 months will be reported with corresponding 95% CI.

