**Time to Progression (TTP)**

TTP is defined as the number of months from the first dose of study drug to tumor progression, which excludes death without tumor progression, by the end of study. TTP of patients who die without documented PD will be censored at date of death. TTP of living patients without documented PD is censored at the same time as PFS, which is the last tumor assessment or the date of first treatment if there is no post-baseline tumor assessment.

Distribution of TTP will be estimated using the Kaplan-Meier method in the Evaluable Population. The median and quartiles of TTP and the TTP rate at 3, 6, 9 and 12 months will be reported with corresponding 95% CI.

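### Primary ORR is defined in all dosed patients but calculated on the Evaluable Population, which drops early failures: ORR and DCR are pushed upward, PFS loses early events, and no all-treated efficacy analysis is planned

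*Protocol*

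**What the plan says.** Protocol 8.5.1 describes ORR as best response "in patients who received at least 1 dose of poziotinib. The ORR will be based on the EP". The first half of that quote corresponds to the Safety Analysis Population (SAF) of Protocol 8.3. The second half names the Evaluable Population (EP), which is smaller.

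Under Protocol 8.3 the EP needs a completed cycle and at least one post-baseline RECIST evaluation. SAP section 4 is narrower, because patients must "complete at least one cycle of poziotinib treatment, and have at least one evaluable post-baseline tumor response evaluation using RECIST criteria". Protocol 8.5.2 names no analysis set for DCR, PFS or TTP. SAP 5.3 does: "All efficacy endpoints will be analyzed based on the Evaluable Population for each cohort". Neither document plans an all-treated efficacy analysis, even as a sensitivity analysis, and SAP 5.1.2 rules out imputation.

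Other rules bear on the point:

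- SAP 5.3.1, on investigator-reported best overall response (BOR): "This includes CR, PR, SD, PD or NE".
- SAP 5.3.3 censors PFS for living patients without progression at the last tumour assessment "or the date of first treatment if there is no post-baseline tumor assessment".
- SAP 5.3.3 on TTP: "TTP of patients who die without documented PD will be censored at date of death".
- Protocol 5.3.8 lists for the End-of-Treatment Visit: "Tumor assessment (unless the patient has documented disease progression or has undergone a tumor assessment within the previous 6 weeks".
- Protocol 8.1, as background to the sample size: "Published ORRs reported for these regimens are 43.6%, 30.8%, and 24%, respectively", for T-DM1, lapatinib-capecitabine and neratinib.
- SAP 5.2.1 reports the numbers in the SAF and in the EP.

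**The concern.** A primary endpoint needs one denominator, and two adjacent sentences give it two. The SAP settles on the EP, and membership of the EP depends on what happens after treatment starts. A patient with no evaluable post-baseline scan cannot be a responder, so removing that patient can only raise ORR. Patients whose toxicity does not stop them, or whose progression is seen on a scan after Cycle 1, stay in. Those whom the drug or schedule fails earliest go out.

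The window for exclusion is real. Cycle 1 lasts 21 days and scans are due every 6 weeks (±14 days), so a patient can stop before any on-treatment scan. If such a patient has an End-of-Treatment scan showing progression, the event is still dropped because the cycle was not completed.

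Two SAP rules do not fit the EP. Censoring at first treatment for patients with no post-baseline scan can never apply to an EP member. Nor can a patient whose assessments are all not evaluable (NE) be in the EP, although the BOR table has a row for that case.

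No hypothesis is tested, so the estimate and its interval are the whole efficacy result. The study also has to choose a dosing schedule, and an efficacy set conditioned on completing Cycle 1 hides the patients for whom a schedule failed early.

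**Working it through.** **Design figure in the documents.** The only design calculation is the superseded one recorded in SAP 3.1: N = 70, ORR 24% against 42%, two-sided exact binomial test. Rejecting at 25 or more, or 9 or fewer, responses gives alpha 0.01854 + 0.01597 = 0.0345 and power 88.3%, which match the stated 0.0345 and 88%. The current plan states no precision for ORR, so there is no current figure to reproduce.

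**Inputs.** Cohort 1 has 32 treated patients (Protocol 8.1). Intervals are exact Clopper-Pearson 95% (SAP 5.3.2). The documents do not give the share excluded (e), the responder counts or the PFS median; those below are assumptions.

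**ORR.** If no excluded patient responds, ORR(EP) = ORR(all treated) / (1 − e). The factor is 1/0.9 = 1.11, 1/0.8 = 1.25 and 1/0.7 = 1.43 at 10%, 20% and 30% excluded. For 32 treated and an assumed 8 responders:

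| Excluded | ORR | 95% CI |
|---|---|---|
| 0 (all treated) | 8/32 = 25.0% | 11.5 to 43.4 |
| 3 | 8/29 = 27.6% | 12.7 to 47.2 |
| 6 | 8/26 = 30.8% | 14.3 to 51.8 |
| 8 | 8/24 = 33.3% | 15.6 to 55.3 |

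A true 24% would read as 30.8% when e = 1 − 24/30.8 = 22.1%. That is the distance between the two lower published rates in Protocol 8.1.

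**DCR.** Assume 18 of 32 have disease control: 56.3% (37.7 to 73.6). If none of the excluded had control, 3, 6 or 8 exclusions give 18/29 = 62.1%, 18/26 = 69.2% or 18/24 = 75.0% (53.3 to 90.2). If 4 of the 8 excluded did have control, the figure is 14/24 = 58.3%. The bias therefore depends on how many of those excluded lacked disease control.

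**PFS.** Take 100 treated patients, 10 of them outside the EP. Of those 10, k have an early event and 10 − k would be censored at first treatment. After the early events, S(all treated) = S(EP) × 90/(90 + k). Assume an exponential all-treated curve with median 4.0 months:

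| k | EP median (months) | EP 3-month PFS |
|---|---|---|
| 0 | 4.0 | 59.5% |
| 5 | 4.3 | 62.8% |
| 10 | 4.6 | 66.1% |

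The all-treated values are 4.0 months and 59.5%. The loss comes only from excluded deaths and documented progressions. Living unscanned patients would add almost nothing, because they are censored at first treatment. TTP changes little, because deaths without progression are censored.

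**Between cohorts.** With a true ORR of 25% in both, equal exclusion shares give no gap. Assumed shares of 20% and 10% give 25/0.80 − 25/0.90 = 31.3 − 27.8 = 3.5 points. The documents do not show which cohort would lose more.

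**The case against.** The best reply is that nobody would be in doubt when programming the analysis: Protocol 8.5.1 ends on the EP and SAP 5.3 repeats it. On this reading the earlier phrase only sets the treated-patient frame. That is fair as a reading, but it leaves the EP as the operative choice, and the EP is the source of the bias.

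Second, a reader can divide the EP responder count by the SAF number from SAP 5.2.1. That approximates all-treated ORR. It gives no planned interval and no all-treated PFS, and it misses any responder outside the EP.

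Third, nothing formal depends on ORR. No hypothesis is tested, cohort continuation rests on Grade 3 or greater adverse events, and the published rates are sample-size background with no planned comparison. This stands. The harm is to the estimate and its interpretation, not to an error rate.

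Fourth, the size is assumed. This also stands: the exclusion share could be small, and the example intervals overlap widely.

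Two smaller points are partly right. NE can occur inside the EP, when a response or stable disease before 6 weeks is followed only by NE, but patients with only NE assessments are still lost. The End-of-Treatment scan can be waived if one was done in the previous 6 weeks. With the visit at its earliest scheduled time, 30 days after the last dose, a screening scan on Day −1 covers only patients who stop by about Day 11. Protocol 4.3 widens this if the visit is brought forward for new treatment.

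Finally, the SAP already reports final enrolment, so changing the primary set now is more than editorial. It does, however, move to the population Protocol 8.5.1 already names, and in the conservative direction.

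**Conclusion.** The concern holds. As written, the plan conditions the primary ORR on events after the start of treatment and removes patients who are almost all non-responders. The direction for ORR is upward. The one exception is a patient who stops in Cycle 1 and responds on a later scan, who leaves both numerator and denominator. DCR is biased upward to the extent that excluded patients lacked disease control. PFS is biased to the extent that they had early events, and TTP is little affected.

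The relative inflation of ORR is 11% to 43% if 10% to 30% of treated patients are excluded, a range assumed because no EP count is given. A distortion between cohorts is possible, but neither its size nor its direction can be shown. The contradiction and the direction for ORR are firm, and only the size is open. Because this is the primary endpoint and no all-treated analysis backs it up, it should be corrected before results are reported.

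**What to change.** In Protocol 8.5.1 and SAP sections 4 and 5.3:

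- Name the SAF (all treated patients) as the primary set for ORR and DCR. Assign BOR of NE to patients with no evaluable post-baseline scan, and count them as non-responders without disease control.
- Run PFS on the SAF, and TTP for consistency. Deaths before the first scan are PFS events. The existing rule of censoring at first treatment then has patients to apply to, namely living patients who were never scanned.
- Keep the EP analyses as supportive, and use one EP definition in both documents, since only the SAP requires an evaluable evaluation.

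The cost is wording in three places, a recorded reason for the change, and one rerun of existing tables. The headline ORR may fall to between 0.9 and 0.7 times the EP figure at the assumed 10% to 30% excluded. No new data are needed.
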